##### **8.5.5.1 Blood samples**

At V2 and V19, a serum pregnancy test must be performed.

If a female subject becomes of childbearing potential during the trial, a serum pregnancy test must be performed as soon as possible or at the latest at the next visit.

##### **8.5.5.2 Urine-sticks**

At V3-V18, urine-stick pregnancy tests will be performed at the site if:

- Pregnancy is suspected
- A menstrual period is missed (unless this is a part of the mode of action of the contraceptive method)
- According to local requirements

Protocol: Liraglutide  
Trial ID: NN8022-4179  
UTN: U1111-1162-7884  
EudraCT no.: 2014-004415-37

~~CONFIDENTIAL~~

Date: 16 July 2020  
Version: 5.0  
Status: Final  
Page: 55 of 125

**Novo Nordisk**

The result of the urine-stick pregnancy test must be documented in the medical record.

### **8.5.5.3 Recording of menstrual periods**

Documentation of the first date of the last menstrual period (if applicable) before V2 must be recorded in subject's medical record.

First date of all menstrual periods since last visit must be collected from all female subjects (section [8.7.3.3](#)) and recorded in the eCRF.

### **8.5.6 Physical examination**

Physical examination must include:

- General appearance
- Head, ears, eyes, nose, throat, neck
- Respiratory system
- Cardiovascular system
- Gastrointestinal system including mouth
- Musculoskeletal system
- Central and peripheral nervous system
- Skin
- Thyroid gland
- Lymph node palpation

Any "abnormal, clinically significant" findings at screening V2 must be recorded as medical history/concomitant illness in the eCRF and in the subject's medical record.

Any clinically significant worsening or new clinically significant findings after V2 must be reported as an AE in accordance with section [12](#).

### **8.5.7 Blood samples for safety assessments**

Any "abnormal, clinically significant" findings at V2 must be recorded as medical history/concomitant illness in the eCRF. The following blood samples must be drawn (for frequency see section [2](#)):

#### **Biochemistry:**

Protocol: Liraglutide  
Trial ID: NN8022-4179  
UTN: U1111-1162-7884  
EudraCT no.: 2014-004415-37

~~CONFIDENTIAL~~

Date:  
Version:  
Status:  
Page:

16 July 2020  
5.0  
Final  
56 of 125

**Novo Nordisk**

- Creatinine
- Creatine kinase (CPK)
- Urea
- Albumin
- Bilirubin, total
- Alanine aminotransferase (ALT)
- Aspartate aminotransferase (AST)
- Alkaline phosphatase
- Sodium
- Potassium
- Calcium, total
- Calcium, albumin corrected
- Amylase
- Lipase

**Haematology:**

- Haemoglobin
- Haematocrit
- Thrombocytes
- Erythrocytes
- Leucocytes
- Differential count:
  - basophils
  - eosinophils
  - lymphocyte
  - monocytes
  - neutrophils

Protocol: Liraglutide  
Trial ID: NN8022-4179  
UTN: U1111-1162-7884  
EudraCT no.: 2014-004415-37

~~CONFIDENTIAL~~

Date: 16 July 2020  
Version: 5.0  
Status: Final  
Page: 57 of 125

**Novo Nordisk**

### **Hormones:**

- Calcitonin (refer to [Appendix C](#) for actions taken if calcitonin is  $\geq 20$  ng/L)
- Prolactin
- Follicle stimulating hormone (FSH)
- Estradiol (females)
- Luteinizing hormone (LH)
- Testosterone (males)
- Thyroid stimulating hormone (TSH)
- Free T4
- Adrenocorticotrophic hormone (ACTH)
- Cortisol
- Dehydroepiandrosterone sulfate (DHEAS)
- Carcinoembryonic antigen (CEA)
- Insulin-like growth factor-1 (IGF-1)

### **Pregnancy test:**

Beta-human chorionic gonadotropin (beta-hCG)

### **8.5.8 Anti-liraglutide antibodies**

Blood samples for determination of anti-liraglutide antibodies are collected from all subjects at randomisation (V3) and at the end of the 16-week double-blind period, see section [2](#). Only samples from subjects treated with liraglutide are analysed for anti-liraglutide antibody development. Depending on the number of subjects in the liraglutide treatment arm, baseline (randomisation V3) from subjects in the placebo group may be analysed for the purpose of determination of the assay cut points. At V19 and V20 antibody samples are collected and analysed from subjects treated with liraglutide only.

Blood samples for the determination of anti-liraglutide antibody must be drawn in a fasting state and prior to administering trial product (see section [2](#)). The anti-liraglutide antibody sample at V20 is to be taken minimum 2 hours after the last meal.

Samples are analysed by the special laboratory for anti-liraglutide antibody formation including cross reactivity to endogenous GLP-1. Furthermore samples from the follow up visit (V20) that are found to be positive for anti-liraglutide antibodies will be analysed for neutralising effect against liraglutide. Anti-liraglutide antibody positive samples from V20 that are also found to cross react with endogenous GLP-1 will in addition be analysed for neutralising effect against endogenous GLP-1. The neutralising antibody analyses will be performed by Novo Nordisk A/S. Baseline antibody samples collected at the randomisation visit will be included in the neutralising antibody analyses for assessment of assay cut points. See further information in sections [8.2](#) and [24.2](#).

Protocol: Liraglutide  
Trial ID: NN8022-4179  
UTN: U1111-1162-7884  
EudraCT no.: 2014-004415-37

~~CONFIDENTIAL~~

Date: 16 July 2020  
Version: 5.0  
Status: Final  
Page: 58 of 125

**Novo Nordisk**

### **8.5.9 Tanner staging**

Pubertal development must be assessed by Tanner staging in accordance with stages 1-5 according to flow chart [2](#). The assessments must be conducted by site staff trained in pubertal assessments. Assessment of testicular volume (by orchidometer) for boys must be included.

Tanner staging can be performed up to 2 weeks before V10 and V19.

Evidence of accelerated pubertal development as judged by the investigator at V2 must be recorded as medical history/concomitant illness in the eCRF and in the subject's medical record.

Acceleration of pubertal development after V3 as judged by the investigator must be reported as an AE in accordance with section [12](#).

Tanner staging is not required once the subject reaches the Tanner stage 5, as judged by the investigator.

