To date, two short-term (5 to 6-week) randomised, controlled trials with liraglutide in paediatric subjects have been completed. In the first trial (NN2211-1800), liraglutide at doses up to 1.8 mg was generally well tolerated in paediatric subjects with T2DM aged 10–17 years. Liraglutide's safety/tolerability and pharmacokinetic profiles in adolescents were similar to those observed in adults with T2DM. In the second trial (NN8022-3967), liraglutide at doses up to 3.0 mg was well tolerated in adolescents with obesity without T2DM (aged 12–17 years); no unexpected safety or tolerability issues were detected. As in adults, liraglutide exposure increased with increasing drug dose. Since no safety/tolerability concerns were raised in the NN8022-3967 trial, a large, long-term trial (NN8022-4180) will investigate the efficacy and safety of liraglutide (doses up to 3.0 mg) for chronic weight management in adolescents with obesity ( $\geq 12$  and  $< 18$  years) and without diabetes type 1.

For an assessment of benefits and risks of the trial, see section [18.1](#), in which a description of preclinical findings includes a dose-dependent delay in sexual maturation in juvenile rats, which was more pronounced in females.

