Dosing in part B will be determined based on the results (including model-estimated steady state exposure) of the NN8022-4181 trial, a PK trial in children with obesity (Tanner stage below 2 (defined as Tanner stage 1 with or without premature adrenarche)), 7-11 years of age (both inclusive), and on the DMC review of PK data and safety data from the 16-week double-blind period from part A of this trial. If the dosing is different than for part A an amendment will be prepared.

Subjects in part A must have Tanner stage 2-5 pubertal development according to inclusion criterion 4. Pubertal development may have been hormonally induced with medical treatment.

Protocol: Liraglutide  
Trial ID: NN8022-4179  
UTN: U1111-1162-7884  
EudraCT no.: 2014-004415-37

~~CONFIDENTIAL~~

Date: 16 July 2020  
Version: 5.0  
Status: Final  
Page: 32 of 125

Novo Nordisk

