Subjects with a history of acute or chronic pancreatitis will be excluded from trial participation. Trial participants will be informed of the characteristic symptoms of acute pancreatitis. Furthermore, serum lipase and amylase activity levels will be monitored on a regular basis during the course of the trial. If pancreatitis is suspected, liraglutide/liraglutide placebo will be discontinued until confirmatory tests have been conducted and appropriate treatment should be initiated. Subjects that are diagnosed with acute pancreatitis must have their trial product withdrawn.

Subjects with a personal or family history of MTC and subjects with Multiple Endocrine Neoplasia Syndrome type 2 are excluded from this trial. In addition, subjects with a screening calcitonin (a specific biomarker for C-cell activation) level  $\geq 50$  ng/L will be excluded from the trial, as hormone concentrations above this threshold are indicative of C-cell neoplasia. During the trial, calcitonin levels will be measured at pre-specified trial visits and levels above upper normal range will be flagged by the laboratory, and reported to the investigator and Novo Nordisk.

It is assumed that the benefits and risks associated with long-term liraglutide treatment will be the same for the paediatric population with PWS as for the adult populations with the exception of any unforeseen effects on growth and pubertal development. In non-clinical studies, dosing liraglutide from post-natal day 21 to 91 in juvenile rats caused a dose-dependent delay in sexual maturation,

Protocol: Liraglutide  
Trial ID: NN8022-4179  
UTN: U1111-1162-7884  
EudraCT no.: 2014-004415-37

CONFIDENTIAL

Date: 16 July 2020  
Version: 5.0  
Status: Final  
Page: 106 of 125

Novo Nordisk

defined in females as age of animals for vaginal opening, and for males as preputial separation (both onset and end) that was most pronounced in females. A delay in age of sexual maturation is known to occur in rats and humans under caloric restriction/increased energy expenditure. Estrous cycle length was slightly extended among high-dose female rats during treatment but returned to normal after two weeks of recovery.

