## Pubertal status

Tanner stage at screening as well as changes in Tanner stage at 16 and 52 weeks will be summarised using descriptive statistics.

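### The puberty-specific reporting rule prompts sites only for acceleration, while the only pubertal signal the protocol cites is a delay in sexual maturation

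*Protocol*

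**What the plan says.** Protocol 8.5.9 contains two reporting instructions specific to puberty.

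- At screening: "Evidence of accelerated pubertal development as judged by the investigator at V2 must be recorded as medical history/concomitant illness".
- After randomisation: "Acceleration of pubertal development after V3 as judged by the investigator must be reported as an AE".

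Neither mentions delay, arrest or regression.

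The non-clinical background points the other way. Section 3.1 refers to "a dose-dependent delay in sexual maturation in juvenile rats, which was more pronounced in females". Section 18.1, under trial-specific risk mitigation, says that "dosing liraglutide from post-natal day 21 to 91 in juvenile rats caused a dose-dependent delay in sexual maturation". The same paragraph assumes that benefits and risks match those in adults, with unforeseen effects on growth and puberty as the one exception.

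For the analysis, SAP 5.4.1.3 says: "Tanner stage at screening as well as changes in Tanner stage at 16 and 52 weeks will be summarised", using descriptive statistics. On the Part A population, Protocol 5.3 notes: "Pubertal development may have been hormonally induced with medical treatment".

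**The concern.** The authors thought a specific instruction on pubertal adverse events was needed and then wrote it for one direction, opposite to the signal they cite. A prompted event is usually captured more completely than an unprompted one. The adverse-event tables would then hold prompted accelerations beside delays that arrive only if an investigator thinks of reporting them. A reader of those tables could not tell an absence of delay from a failure to ask about it, in the one area where the protocol does not assume that paediatric risks match adult risks.

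**Working it through.** The point concerns the direction of a reporting rule, so the check sets the sections side by side.

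**1. Rule against signal.** Both puberty-specific rules in 8.5.9 cover acceleration. The finding in 3.1 and 18.1 is a delay. Neither document explains the asymmetry.

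**2. Does any other section name delay as a reportable event?** No.
- The medical events of special interest in 12.1 are medication errors.
- The events with additional data collection in 12.1 are gallstone disease, neoplasms and pancreatitis.
- The physical-examination items in 8.5.6 do not include pubertal signs.

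**3. Is delay reportable by a general route?** Yes.
- The definition in 12.1 covers any unfavourable and unintended sign, and 12.2 requires every event meeting it to be reported.
- Section 8.3.2 requires all concomitant illnesses to be recorded and clinically significant worsening to be reported.
- Section 8.5.7 includes LH, FSH, estradiol and testosterone. Section 8.2.2 requires each out-of-range result to be classed as clinically significant or not, and 12.1 makes clinically significant abnormalities adverse events.

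**4. How strong is that route for a stalled puberty?** Weaker than a direct prompt. Sections 3.1 and 6.7 describe hypogonadism as a feature of the syndrome, and 12.1 says that pre-existing conditions are not adverse events unless they worsen. A stall is easily put down to the syndrome. Tanner stage is recorded at V2, but sites are not asked to note at that visit that puberty is already delayed, which would help in judging later worsening.

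**5. What do the non-event data offer?**
- Collected: Tanner stage, testicular volume in boys (8.5.9), dates of menstrual periods (8.5.5.3) and sex hormones (8.5.7).
- Planned in the SAP: descriptive Tanner summaries, hormone shift tables and listings of abnormal values, height velocity (5.4.1.3), and a listing of LH, FSH and testosterone with reference ranges (6.2.3).
- Limits: no definition of delay or expected rate of progression is given. SAP 5.4.1.3 names no analysis of testicular volume or menstrual dates. SAP 6.2.3 drops testosterone change from baseline in Part B because of an assay change.
- SAP 5.1 reports Part A, Part B and all subjects, but does not separate subjects with induced puberty within Part A. By Protocol Table 17–2, Part A plans 22 liraglutide and 11 placebo subjects. One subject is therefore 1/22 = 4.5% of one arm and 1/11 = 9.1% of the other, and a few induced subjects can move the summary. How many there are is not stated.

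**6. How many subjects are concerned?** Table 17–2 gives 22 + 16 = 38 planned on liraglutide and 11 + 8 = 19 on placebo. Part A admits Tanner stages 2–5. Staging is not required once stage 5 is reached, and no further progression can then be delayed. Part B admits Tanner stage 1 from age 6, where absence of puberty over 52 weeks would often be unremarkable. The informative number is below 38, and the documents do not allow it to be counted.

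**The case against.** The strongest reply is that 8.5.9 adds an example to a general duty and does not narrow it. A delay that an investigator judges untoward must be reported under 12.1 and 12.2. The acceleration rule is itself left to investigator judgement, and several other data streams could reveal a stall. This stands, and it rules out four stronger readings that a reader might infer.

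- *That delay would not be reported as an adverse event, or that 8.5.9 is the only mandatory trigger.* The general definition, the worsening rule and the laboratory rule all still apply.
- *That delay is a harm the protocol predicts in children.* It is a juvenile-rat finding and is not listed under potential risks in 18.1. For children the protocol speaks of unforeseen effects and gives no direction.
- *That all 38 liraglutide subjects are at unmonitored risk.* Many could not show a delay within the trial, and Tanner stage and hormones are followed.
- *That the data monitoring committee would not see a delay.* Section 12.7.2 gives it safety data on an ongoing basis and leaves the content to a charter that is not among the documents.

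The concern about induced puberty also applies to Part A only. Part B is reported separately, and induction is mentioned only for Part A.

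None of this explains why the specific prompt covers one direction, and the wrong one relative to the cited finding.

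**Conclusion.** The point holds as an asymmetry of ascertainment. Section 8.5.9 asks about acceleration. The cited signal is delay, which is left to the general adverse-event definition and to descriptive summaries. The likely effect is that adverse-event tables capture acceleration more fully than delay. Its size cannot be computed, because the documents give neither the number of subjects able to show a delay nor the number with induced puberty.

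The conclusion assumes that a specific prompt raises reporting, and that a stall in this syndrome is more readily attributed to existing hypogonadism than reported. Both are reasonable, but neither is shown by data in the documents. This is a cheap improvement in safety ascertainment that should be made. It is not a failure to monitor puberty.

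**What to change.** **Protocol 8.5.9.** Reconcile it with 18.1. Widen both the V2 history entry and the post-V3 adverse-event rule to cover acceleration or delay, arrest or regression of pubertal development, as judged by the investigator.

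**SAP 5.4.1.3.** Show the Part A summaries of Tanner change and of LH, FSH, estradiol and testosterone separately for subjects with and without sex-hormone treatment. Protocol 8.3.3 already records the name, indication, and start and stop dates of concomitant medication, so no new data are needed. The indication lets contraception be told apart from induction of puberty. Treatment status at baseline is the safer basis for the split, with starts during the trial listed, since a start could itself be a response to a stall.

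**Cost.** A wording change in 8.5.9 and one extra split in tables already planned. A protocol change can act only on visits still to come, whereas the SAP split works on data already collected. Some delay reports will reflect the hypogonadism of the syndrome. The concurrent control arm (planned 19 subjects, on placebo to week 16 and untreated to week 52) gives the background rate. After week 16 allocation is known, so investigator-judged reports are less protected from bias.

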### **8.5.10 Mental health questionnaires (part A only)**

The mental health of subjects will be assessed by the following questionnaires to meet the regulatory requirements (section [2](#)):

- Columbia Suicide Severity Rating Scale (C-SSRS) Pediatric/Cognitively Impaired questionnaire
- Patient Health Questionnaire 9 (PHQ-9) for children and adolescents. The questionnaires will be available in a linguistically validated paper version.

Drugs for weight loss are one of the non-psychiatric drugs for which treatment-emergent suicidal ideation and behaviour as well as depression must be surveyed. Even though liraglutide has not been associated with suicidality or depression the two mental health questionnaires, C-SSRS and PHQ-9 have been included in part A of the present trial.

The questionnaires must be filled in and data must be entered into the eCRF. In case questionnaires cannot be completed because of mental incapacity, this must be documented in the subject's medical record and the eCRF.

#### **8.5.10.1 C-SSRS**

The investigator or delegated staff must complete the C-SSRS based on an interview with the subject. The investigator or delegated staff interviewing the subject must complete an online interviewer training prior to first interview.

The questionnaires completed at V2 must be used to exclude subjects from the trial with any suicidal ideation of type 4 (active suicidal ideation with some intent to act, without specific plan) or type 5 (active suicidal ideation with specific plan and intent).

Protocol: Liraglutide  
Trial ID: NN8022-4179  
UTN: U1111-1162-7884  
EudraCT no.: 2014-004415-37

~~CONFIDENTIAL~~

Date: 16 July 2020  
Version: 5.0  
Status: Final  
Page: 59 of 125

**Novo Nordisk**

### **8.5.10.2 PHQ-9**

The PHQ-9 should be completed by the subject without interruption.

The questionnaires completed at V2 must be used to exclude subjects with a PHQ-9 score  $\geq 15$  from the trial.

The investigator or delegated staff must review questionnaires for completeness and adverse events immediately following administration. The review must be documented in the subject's medical record. If clarification of entries or discrepancies in the questionnaire is needed, the subject must be questioned and a conclusion made in the subject's medical record. Care must be taken not to bias the subject.

### **8.5.10.3 Referral to mental health professional**

If a subject has a PHQ-9 score from 10-14 both inclusive on any questionnaire the subject should be referred to a mental health professional (MHP) if judged relevant by the investigator. If referral is not deemed relevant, this must be documented in the subject's medical record.

A subject must be referred to a MHP if the subject has:

- a PHQ-9 score  $\geq 15$  or
- any suicidal behaviour or
- any suicidal ideation of type 4 or type 5 on any C-SSRS assessment
- if the opinion of the investigator it is necessary for the safety of the subject

If one or more of the above referral criteria are met the investigator should explain to the subject and/or the subject's LAR why the referral and psychiatric evaluation by a MHP is needed. If the subject and/or the subject's LAR refuses to be referred to a MHP, the decision should be documented in the medical record and the investigator must assess, if it is safe for the subject to continue in the trial, or if the subject should be discontinued from trial product (section [6.4](#) and [8.1.8](#)).

If a subject's psychiatric disorder can be adequately treated with psycho- and/or pharmacotherapy, then the subject, at the discretion of the investigator (in agreement with the MHP), may continue in the trial. Otherwise, the trial product must be discontinued (section [6.4](#) and [8.1.8](#)).

Protocol: Liraglutide  
Trial ID: NN8022-4179  
UTN: U1111-1162-7884  
EudraCT no.: 2014-004415-37

~~CONFIDENTIAL~~

Date: 16 July 2020  
Version: 5.0  
Status: Final  
Page: 60 of 125

**Novo Nordisk**

## 8.6 Additional safety assessments

### 8.6.1 In case of elevated calcitonin

If any calcitonin value post randomisation is above upper normal limit a repeated measurement of calcitonin should be taken within 4 weeks. All cases  $\geq 20$  ng/L will be reviewed by an external expert who will provide recommendations to the investigator whether further evaluation is indicated. For details, refer to [appendix C](#).

### 8.6.2 Suspicion of acute pancreatitis

In case of acute, severe persistent abdominal pain leading to a suspicion of acute pancreatitis, the trial product should promptly be interrupted until the diagnosis of pancreatitis can be excluded. Appropriate additional examinations must be performed. Measurement of serum amylase and lipase activity levels must be done locally. If acute pancreatitis is ruled out, trial product should be re-initiated on same dose as when trial product was interrupted.

Pancreatitis is confirmed if as a minimum 2 of 3 criteria are met:

- Severe acute abdominal pain
- Serum amylase and/or lipase  $>3\times$  upper normal limit
- Characteristic findings on relevant imaging e.g. computerised axial tomography/magnetic resonance imaging/ultrasound

If diagnosis of pancreatitis is confirmed the trial product must be discontinued (sections [6.4](#) and [8.6.3.3](#)) and appropriate treatment(s) and careful monitoring of the subject should be initiated.

